2.3. Exploratory Objectives

- To evaluate changes in proteomic and immune biomarkers from Baseline

3. INVESTIGATIONAL PLAN

3.1. Overall Study Design

This is a multi-center, randomized, double-masked, placebo-controlled Phase 2 study to evaluate the ocular hypotensive efficacy, safety, and tolerability of SBI-100 Ophthalmic Emulsion after 7 days of binocular dosing, twice daily (BID).

The study will be conducted in 54 patients with elevated intraocular pressure at approximately 6 clinical research centers in the United States.

The study includes a 35-day screening period, which encompasses a wash-out (if needed), followed by a visit on Day-1 to confirm eligibility and provide baseline diurnal IOP, followed by a 14-day double-masked treatment period entailing topical BID dosing. The end of study (EOS) assessments will be performed within 2 days of the last dose on Day 14. Dosing will occur each day in the morning and in the evening 12 hours after the morning dose.

Study visits will occur on Days -35 to Day -2 (Screening), Day-1, Day 1, Day 7, Day 14, and (if not completed on Day 14) End of Study/Early Termination (EOS/ET).

At Screening, eligible patients will be asked to wash-out of their current IOP-lowering therapy (if currently using). Patients requiring wash-out will return for Day-1 at the completion of their wash-out, in accordance with the type of IOP-lowering therapy used. Patients who are treatment naïve may return upon confirmation of screening eligibility. On Day-1, diurnal IOP will be measured at 08:00 (± 30 m), 10:00 (± 30 m) and 16:00 (± 30 m) hours. If eligible, patients will be asked to return the following day to perform Day 1 procedures.

The first dose will occur in clinic on Day 1 with Investigation Product (IP) administered by the site staff in the morning immediately after the 08:00 IOP measurement and randomization via Interactive Response Technology (IRT). Subsequent study assessments up to 8 hours post-dose will be performed. The evening dose will be self-administered by the patient in the evening of Day 1 approximately 12 hours after the AM dose (~ 20:00) and continued for both mornings and evenings on Days 2 through 6.

Patients will return to the clinic on the morning of Days 7 and 14 for site administration of the morning dose with assessments up to 8 hours post-dose. The Day 7 evening dose will be self-administered by the patient in the evening approximately 12 hours after the AM dose (~ 20:00) and continued for both mornings and evenings on Days 8 through 13.

When patients return to the clinic on Day 14 for site administration of the morning dose with assessments up to approximately 14 hours after the AM dose. The Day 14 evening dose (final dose) will be administered on-site with subsequent exit procedures performed. If EOS/ET procedures cannot occur on Day 14 (due to scheduling conflicts, site hours, etc.,) the Day 14 PM dose can be self-administered, with the patient returning within 2 days of Day 14 for EOS procedures (see Table 2).

IOP efficacy will be evaluated by Goldmann applanation tonometry. Safety/tolerability will be evaluated by review of ocular signs and symptoms through BCVA, ophthalmic assessments, ocular comfort PRO, vital signs, and other standard safety measures.

3.1.1. Number of Patients

There will be 54 patients with elevated intraocular pressure.

3.2. Measures to Minimize Bias:

3.2.1. Randomization/Masking

Patients will be randomized in a 1:1:1 ratio into 1 of 3 study treatments, via IRT. The identity of treatments will be masked to all patients and clinical sites. IRT will be programmed with mask-breaking instructions in the case of an emergency (6.2).

3.2.2. Determination of Study Eye

The study eye will be determined for efficacy analysis purposes. Both the study eye and the fellow eye will be analyzed for safety. The study eye will be determined through statistical programming to select the eye with the highest mean diurnal IOP from the measures taken on Day-1 (baseline). In the case of a tie, the study eye will be the right eye (OD).

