2.1.2. Efficacy Endpoints

- Change from Day-1 in mean diurnal IOP at Day 14, in the study eye (see [3.2.2](#)) for 0.5% SBI-100 Ophthalmic Emulsion compared to placebo
- Change from Day-1 in mean diurnal IOP at Day 14, in the study eye (see [3.2.2](#)) for 1.0% SBI-100 Ophthalmic Emulsion compared to placebo

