4. SELECTION AND WITHDRAWAL OF PATIENTS

4.1. Inclusion Criteria

Patients must meet all the following inclusion criteria to participate in this study:

1. At least 18 years of age or greater at time of informed consent.
2. Diagnosis of either primary open angle glaucoma (POAG) or ocular hypertension (OHT) in each eye.
3. Intraocular Pressure (IOP) Criteria:
 - a. If currently on an IOP-lowering therapy, patient is willing to withhold therapy according to study requirements, and in the opinion of the Investigator, can do so without significant risk.
 - b. If treatment naïve, Screening IOP is ≥ 21 and ≤ 36 mmHg in each eye, and in the opinion of the Investigator, is likely to be controlled on a single IOP-lowering therapy.
 - c. 08:00 Hour IOP is between 21 and 36 mmHg in each eye on Day-1 and Day 1.
4. Central corneal thickness between 480 and 620 μm at Screening in each eye.
5. Best correct visual acuity (BCVA) for distance equivalent to 20/100 or better in each eye at Screening and Day 1 (pre-dose).
6. Able to give signed informed consent and follow study instructions.
7. If patient and/or partner has reproductive potential, agrees to use reliable methods of contraception throughout their participation in the study and until at least 30 days after the last dose.
 - a. If female of childbearing potential, has a negative pregnancy test at Screening and Day-1.

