6. INVESTIGATIONAL PRODUCT/STUDY TREATMENT

6.1. Description of Investigation Product/Study Treatment

Table 3: Study Treatment/Investigational Product

Investigational Product/Study Treatment*			
Product Name:	0.5% (5 mg/mL) SBI-100	1.0% (10 mg/mL) SBI-100	Placebo **
Dosage Form:	Sterile Ophthalmic Emulsion for Topical Administration		
Unit Dose	0.3 mL single use vial (1 vial per dose, applied binocularly)		
Route of Administration	A single drop (approximately 30 µL) applied in each eye (binocularly) BID		
Physical Description	White/opaque sterile emulsion containing SBI-100 (THC-valine- hemisuccinate with emulsion carbomer) at pH 3.5 to 4.5	Matching sterile emulsion without active drug	
Manufacturer	NextPharma-Tampere Oy, Tampere, Finland (manufacturing and testing), with QA and release by Skye		

*Throughout this document investigational product will be referred to as “Study Treatment”. The term study treatment is a generalized reference to any IP for this study, encompasses all dose levels and the matching placebo.

**Placebo has a matching formulation to the active treatment but does not include active drug.

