7. STUDY VISITS

Where possible, assessments should be conducted in order of least invasive to most invasive.

All ophthalmic assessments will be performed in each eye. Assessments within a visit should occur in the order noted below. Additional instructions on study assessments will be provided within the study procedure manual.

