8.3.4. Intraocular Pressure

IOP measurement should be conducted after the biomicroscopy exam is completed and prior to pupil dilation, as applicable. IOP will be measured using a Goldmann applanation tonometer, using a masked-examiner method. A 2-person reading method will be used for all IOP measures wherein 1 person adjusts the dial in a masked fashion and a second person reads and records the reading. All pressure will be recorded in mmHg. Two consecutive measurements are taken in each eye and recorded as the mean of the two measurements. If the two measurements differ by >1.0 mmHg, a third measurement is performed, and the median is recorded.

As IOP measurements vary throughout the day, Day-1 will provide a baseline diurnal IOP for patients. Serial IOP measurements must be performed within time windows.

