10. STATISTICS

10.1. Determination of Sample Size

From prior studies, the expected standard deviation (SD) of diurnal IOP in each treatment group ranges from 2.0 to 3.0 mmHg, with an average of 2.7 mmHg. The following estimates rely on a conservative SD of 3.0 mmHg for all visits and time points.

Analyses will be performed using a 2-sided alpha level of 0.05 for each test. For this feasibility study, no adjustments will be made for multiple comparisons across the multiple treatment groups versus the control group, or across tests for multiple visits and time points.

Sample sizes for both 80% and 90% power, and assuming a pooled SD of 3.0, are shown. The table below summarizes the sample size requirements for various expected differences in mean diurnal IOP between the active treatments and placebo. Sample sizes are shown prior to considering dropouts or non-compliance for the various endpoints and assumptions.

Table 5: Sample Size Requirements

Endpoint: Superiority of treatment over placebo for change from baseline (Day-1) at Day 14; SD = 3.0		
	Power	
	80%	90%
Difference (SBI-100 – Placebo) = 3.0	17	23
Difference (SBI-100 – Placebo) = 3.5	13	17
Difference (SBI-100 – Placebo) = 4.0	10	13

For this feasibility study, a difference of 3.0 mmHg in mean diurnal IOP between treatment and placebo is assumed with 80% study power.

Accounting for up to 5% dropout over a short-term study, an additional ~5% will need to be enrolled in each treatment group. For an expected difference of 3.0 mmHg at 80% power, $17/95\% = 18$ patients per treatment group will need to be enrolled, for a total of 54 patients in this 3-treatment group study.

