10.4.2. Primary Endpoint

The primary analysis will compare the change from baseline (Day-1) in mean diurnal IOP at Day 14 for each of the SBI-100 treatment groups to the placebo group. ANCOVA will be used for each comparison at a two-sided alpha level of 0.05 without any adjustment as described in [10.4.6](#). The model will include adjustment for the baseline value. The primary efficacy analysis will be based on the ITT population.

The null hypothesis for the primary endpoint is as follows:

The change from baseline (Day-1) in mean diurnal IOP of each dose level of SBI-100 Ophthalmic Emulsion will not be different from that of its placebo after 14 days of BID dosing.

For this feasibility study, the primary analysis will be based on observed data only, not imputing missing data. If the study eye is missing data on Day 14, the mean diurnal IOP will not be calculated for the primary analysis to avoid using a biased estimate. Thus, the while-on-treatment strategy for handling intercurrent events of early discontinuation will be employed.

The actual mean diurnal IOP values at each visit will be analyzed with MMRM.

Sensitivity analysis will be described *a priori* in the SAP and will include analyses on the Per Protocol population should there be a significant number of major protocol deviations. In the case of >5% of patients with missing data for any time point, the primary analyses will be repeated on the ITT population with imputed missing data (at the visit and time point level) following other intercurrent event strategies. Other methods for defining the study eye and analyzing both eyes in a random effects model may also be considered.

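### Does basing the primary endpoint on the higher-pressure eye, when both eyes are treated and measured, waste power the trial needs?

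*Protocol*

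**What the plan says.** Protocol 2.1.2 defines the primary efficacy endpoint, for each dose against placebo, as "Change from Day-1 in mean diurnal IOP at Day 14, in the study eye". Section 3.2.2 has statistical programming "select the eye with the highest mean diurnal IOP from the measures taken on Day-1 (baseline", and the right eye is taken if the eyes tie. The Synopsis and 10.4.1 give the same rule. Section 3.2.2 also says that both eyes are analysed for safety.

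The two eyes are otherwise handled alike:

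- Entry (4.1): "08:00 Hour IOP is between 21 and 36 mmHg in each eye on Day-1 and Day 1".
- Dosing (6.1): a single drop "applied in each eye (binocularly) BID".
- Assessment (7): "All ophthalmic assessments will be performed in each eye".
- Tonometry (8.3.4): "Two consecutive measurements are taken in each eye and recorded as the mean of the two measurements", with a third reading if those two disagree by more than 1.0 mmHg.

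In its paragraph on sensitivity analyses, 10.4.2 adds: "Other methods for defining the study eye and analyzing both eyes in a random effects model may also be considered". Section 10.1 sizes the trial on an SD of 3.0 mmHg, described as conservative because the SD in prior studies "ranges from 2.0 to 3.0 mmHg, with an average of 2.7 mmHg". It states no inter-eye correlation.

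**The concern.** There is no untreated control eye, and each eye passes the same entry limits, gets the same product and is measured at the same times. Half of the eye-level IOP readings then stay out of the primary analysis, and the protocol gives no reason. Two correlated readings per patient normally estimate a treatment effect more precisely than one. The plan sits close to its 80% target with only 18 patients enrolled per arm, so a few points of power at no recruitment cost look worth having.

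There is a second issue. The eye is chosen on the Day -1 reading that also serves as its baseline. The higher of two noisy values tends to fall on remeasurement, so changes from baseline within each arm, placebo included, will look somewhat larger than they are.

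If this were a real fault, the trial would be giving up precision on its main result, and its single-arm changes would be read too favourably.

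**Working it through.** **Inputs from the protocol (10.1, 3.2.1):** two-sided alpha 0.05 per comparison, difference 3.0 mmHg, SD 3.0 mmHg, 1:1:1 allocation, 17 evaluable per arm. **Assumed, not in the protocol:** inter-eye correlation r = 0.5, 0.7, 0.8 or 0.9; equal SD and equal effect in both eyes; a Day -1 to Day 14 correlation where stated.

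**1. The plan's own figure.** A two-sample t-test (noncentral t, 2n − 2 degrees of freedom) gives 17 per arm at 80% power and 23 at 90% for 3.0 mmHg, 13 and 17 for 3.5, and 10 and 13 for 4.0. That matches every cell of Table 5. With dropout, 17/0.95 = 17.9, so 18 per arm and 54 in total. Power at 17 per arm has noncentrality 3.0/(3.0 × √(2/17)) = 2.915 and equals 80.7%. At the average SD of 2.7 it is 88.1%.

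**2. The two-eye mean.** Its SD is 3.0 × √((1 + r)/2). The 95% CI half-width is t(0.975, 32) × SD × √(2/17), with t = 2.037. For one eye this is 2.10 mmHg.

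| r | SD, two-eye mean | Power, n = 17 | CI half-width (mmHg) |
|---|---|---|---|
| 0.5 | 2.60 | 90.4% | 1.82 |
| 0.7 | 2.77 | 86.6% | 1.93 |
| 0.8 | 2.85 | 84.6% | 1.99 |
| 0.9 | 2.92 | 82.6% | 2.04 |

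So the nominal gain is real, between about 2 and 10 points, and it goes to zero as r approaches 1.

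**3. Under the planned analysis.** The primary test is ANCOVA with baseline adjustment (10.4.2), not a t-test on unadjusted values. Simulated with higher-eye selection, an SD of 3.0 per eye and visit, and no truncation by the entry limits:

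| Day -1 to Day 14 correlation | One eye | Two-eye mean, r = 0.5 / 0.7 / 0.8 / 0.9 |
|---|---|---|
| 0.5 | about 89% | 95.7 / 93.4 / 92.4 / 90.9% |
| 0.7 | about 97% | 99.4 / 98.8 / 98.3 / 97.7% |

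With no correlation between visits, one eye gives about 78–80% and the two-eye mean 81–90%. Type I error was 0.049 to 0.054 for both analyses in the runs with correlation 0.5, so choosing the higher eye does not upset the test.

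**4. If the fellow eye responds less.** With 3.0 mmHg in the higher eye, the two-eye mean breaks even when the fellow-eye effect is 2 × 3.0 × √((1 + r)/2) − 3.0. That is 2.20, 2.53, 2.69 and 2.85 mmHg at r = 0.5, 0.7, 0.8 and 0.9. With a fellow-eye effect of 2.5 mmHg, power is 84.9, 80.3, 78.0 and 75.8%; the last three are below the one-eye 80.7%.

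**5. If fellow-eye readings are missing.** The Synopsis voids the mean diurnal IOP when the study eye lacks any Day 14 time point, and 10.4.2 has a similar rule. If that extended to both eyes, one further patient lost per arm at r = 0.9 gives 80.2% (n = 16), and two lost at r = 0.8 give 79.6% (n = 15). Both are below the one-eye 80.7% at n = 17.

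**6. Regression to the mean from the eye choice.** The higher of two eyes exceeds the mean by SD × √((1 − r)/π). The spurious fall is (1 − visit correlation) times that. At visit correlation 0.5 this is 0.5 × 3.0 × √((1 − r)/π) = 0.60, 0.46, 0.38 and 0.27 mmHg at r = 0.5, 0.7, 0.8 and 0.9. The same rule applies in every arm on pre-dose data, so the expected artefact is equal across arms and drops out of each comparison with placebo.

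**The case for a change.** The best case for a change is that the sponsor has paid for the fellow-eye readings and leaves them out of the primary estimate. In information terms the two-eye mean is worth 17/((1 + r)/2) patients per arm: about 22.7 at r = 0.5 and 17.9 at r = 0.9. In a small proof-of-concept study a narrower interval is useful. Both eyes meet the same entry limits, so a similar response is a fair working assumption. The endpoint eye is fixed in the protocol itself and so cannot simply be left to the SAP, and the both-eye model is only permitted, not promised.

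Part of this stands. If r is moderate and both eyes respond alike, a both-eye primary would be somewhat more precise, and a statistician designing the trial afresh could reasonably prefer it. The within-arm changes should also be read with the regression effect in mind. Averaging would remove the eye-choice part but not the part caused by the 21 mmHg entry limit.

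It does not show that the protocol fixes anything badly. The higher-pressure eye and the average treated eye are different targets of estimation, and a trial of a pressure-lowering drug may legitimately choose the former. Moving to the average would alter the primary endpoint, probably by protocol amendment under 10.4, and would need a rule for a missing fellow-eye reading. The lesser step, making the both-eye model a firm supportive analysis, concerns an analysis that the Synopsis and 10.4.2 already name. Section 10.4.2 leaves the description of sensitivity analyses to the SAP, which is not at hand.

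**Conclusion.** The concern does not hold. The study-eye rule is objective, applied to pre-dose data, complete with a tie rule, and the same in the Synopsis, 3.2.2 and 10.4.1. The one-eye comparison is valid and unbiased between arms. It reaches the stated target: 80.7% at an SD of 3.0 and 88.1% at 2.7, before any benefit from baseline adjustment.

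What remains is a design preference. The t-test gain of about 2 to 10 points depends on an assumed inter-eye correlation of 0.9 to 0.5, an equal effect in both eyes and no extra missing data. Under ANCOVA it is about 2 to 7 points at a visit correlation of 0.5 and about 1 to 2 points at 0.7. Small departures from the equal-effect or missing-data assumptions cancel it when the eyes are highly correlated. The eye-choice artefact of roughly 0.3 to 0.6 mmHg (visit correlation 0.5) affects only within-arm changes and cancels against placebo. Nothing in the protocol is wrong or contradictory on this point, and no change is called for.

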3.3. Study Design Rationale

3.3.1. Design Rationale

SBI-100 is being developed for reduction of IOP in patients with POAG and OHT. It is expected to act through a novel mode of action (CB1 agonism) that leads to an increase in TM outflow, thus reducing IOP. SBI-100-201 is a proof-of-concept study for a topical ophthalmic emulsion formulation of SBI-100. Up to two different concentrations (0.5% and 1.0%) will be explored to evaluate the ocular hypotensive efficacy of SBI-100 Ophthalmic Emulsion, along with safety and tolerability. As a secondary objective, the study will also aim to characterize the pharmacodynamics of SBI-100 Ophthalmic Emulsion using IOP as a pharmacodynamic biomarker. Ocular comfort and psychotropic effects of SBI-100 will also be explored as a secondary objective.

3.3.2. Criteria for Dosing

Eligible patients will be randomized to in a 1:1:1 ratio into 1 of 3 treatment groups:

- 0.5% (5 mg/mL) SBI-100 Ophthalmic Emulsion
- 1.0% (10 mg/mL) SBI-100 Ophthalmic Emulsion
- Placebo Ophthalmic Emulsion

The proposed levels are based on the nonclinical toxicology, which demonstrated a No Observed Adverse Effect Level (NOAEL) of 1.0% BID in rabbit (binocular administration of 50 μ L per drop) which represents a total dose of 1.0 mg/mL SBI-100 in each eye or 2.0 mg/mL per day. For this study, the single-unit dose dropper will deliver approximately 30 μ L per drop.

Therefore, the lower dose of 0.5% will deliver approximately 0.30 mg/mL SBI-100 in each eye, or 0.60 mg/mL per dose. This low dose offers 3.3 times margin of safety to doses that have shown to be relatively well tolerated in toxicological species.

3.4. End of Study Definition

[figure not shown]
The EOS is defined as the date of a patient's last procedure was performed for this study. EOS procedures are to be performed after the PM dose on Day 14. If these procedures cannot be performed on Day 14, the patient will self-administer the PM dose and return to the site within 2 days for the EOS/ET visit.

A patient is considered to have completed the study if he/she completes all the in-clinic visits (Days -1, 1, 7 and Day14) and all assessments listed in the EOS/ET visit.

If a patient withdraws from the study earlier than planned, the assessments listed within the EOS/ET visit should be performed.

3.5. Criteria for Study Termination

The Sponsor reserves the right to discontinue the study at any time for clinical or administrative reasons.

Figure 1: Study Design

*Day 14 (PM dose) to occur on-site with EOS procedures following. If EOS procedures cannot occur post-PM dose on Day 14 (PM dose), the patient may self-administer at home and will return for EOS/ET within 2 days.

Table 2: Schedule of Assessments

	Visit 1	Visit 2	Visit 3		Visit 4		Visit 5	Visit 5a	
If not treatment naïve must wash-out of IOP-lowering therapy prior to Day-1.	Screening / Wash-out (D-35 to -2)	Day -1	Day 1		Day 7		Day 14	EOS/ ET (D 14+2)	Day 14 – PM dose to occur on-site with EOS procedures following. Patient to self-administer PM dose if EOS procedures to occur on separate day. Procedures listed in EOS/ET are to be performed for any early terminations
Informed Consent	X								
Demographics	X								
Medical/Ophthalmic/Surgical Hx	X	X							Confirm changes from screening at Day-1
Inclusion/Exclusion	X	X	X						Specific criteria must be confirmed at Day-1 and Day 1 (pre-dose)
BCVA & Pupil Diameter	X		X		X		X	X	Screening: baseline manifest refraction included with VA Post-dose BCVA with ≥ 2 log line drop requires further assessment (repeat MR, assessment of AE, etc.)
Slit Lamp Biomicroscopy	X		X		X		X	X	Screening: includes gonioscope
Biomarker Collection - Blood		X					X		May be performed anytime during the Day -1 visit, anytime after dosing during the Day 14 visit.
Biomarker Collection - Tears		X					X		Performed at 10:00 (± 30 m) and must be performed at least 10 minutes prior to IOP measurement within time window
Intraocular Pressure (IOP)	X	S	S		S		S	X	Serial: 08:00 (± 30 m), 10:00 (± 30 m) and 16:00 (± 30 m). IOP is to be measured at the same time on visit days as Day-1.
Central Corneal Thickness	X							X	
Vital Signs	X		X		X		X	X	Performed after 5 mins of rest. Blood pressure, heart rate and respiratory rate.
Dilated Fundoscopy	X							X	
Visual Field	X							X	Results within 3 months of screening used for entry if using automated threshold visual field (24-2 or SITA Fast) and considered reliable
Safety Labs	X							X	Includes – chemistry, hematology, and urinalysis.
Pregnancy Test	X	X						X	For females of childbearing potential. Serum at Screening, urine at visits 2 and 5a.
Drug/Alcohol Screen	X	X							Testing will be repeated once prior to randomization to confirm a positive test at screening or day -1.
Randomization			X						Via IRT after 08:00 IOP confirms eligibility
On-site Dosing			X		X		X		AM dose administered following 08:00 IOP. Treatment provided as a single use vial for binocular instillation BID. AM around 08:00 and PM around 20:00. Dose should be separated by 12 hours. Patient may self-administer PM dose on days 1 and 7.

	Visit 1	Visit 2	Visit 3	Visit 4	Visit 5	Visit 5a	
If not treatment naïve must wash-out of IOP-lowering therapy prior to Day-1.	Screening / Wash-out (D-35 to -2)	Day -1	Day 1		Day 7	Day 14	Day 14 – PM dose to occur on-site with EOS procedures following. Patient to self-administer PM dose if EOS procedures to occur on separate day. Procedures listed in EOS/ET are to be performed for any early terminations
Ocular Comfort PRO			S	S	S		Applies to AM dose occurring on-site. Pre-dose and immediately after drop instillation up to 2 mins, 5m±2m and 10m±5m post-dose. If at 10 min, PRO rating has not returned to the visit day pre-dose value, administer every 30 minutes until pre-dose value is achieved.
Kit Dispensing /Return			D	D/R	R	R	Day 1: patient education on drop instillation, handling, and storage. Return: used and un-used vials must be returned. Dispensing: discuss with the patient IP expectations and diversion prevention. Return: Staff must review with the patient vial level use and determine reasons for missed doses.
Prior/Concomitant Medications	X	X	X		X	X	
Adverse Events	X	X	X		X	X	Assessments performed outside of scheduled visits due to an adverse event should be captured as unscheduled visits.

H = hour (s), m = minute(s), S = serial procedures, D = Dispense, R = Return

